Following these encouraging preclinical studies, safety and tolerability of Revacept was investigated in a first-in-man study (Ungerer et al., 2011). In a phase I clinical trial, 30 male human volunteers received a single intravenous dose of Revacept ranging between 10-160 mg. All investigated doses were well tolerated and no drug-related side effects occurred. Moreover, no anti-Revacept antibodies were produced and favourable pharmacokinetic and pharmacodynamic profiles were observed. In summary, results from both preclinical studies and the phase I clinical trial constitute a solid basis for proceeding to a clinical trial in the target patient population. The study presented here aims to demonstrate both safety and evidence of efficacy of Revacept treatment in patients suffering from symptomatic carotid stenosis.

Dose selection rationale

Detailed background information on preclinical pharmacology, pharmacokinetics, toxicology and on the phase I clinical study of Revacept is provided in the Investigator Brochure. When 10 – 160 mg Revacept were administered during a phase I clinical trial, maximal pharmacodynamic effects were measured *ex vivo*, starting at 40 mg, and no drug-related adverse events occurred. Pharmacokinetic studies demonstrated that the area under the curve and maximum concentration proportionally increased with higher dose levels. Because no maximum tolerated dose (MTD) was defined for the adult population and with data generated during preclinical and phase I studies we propose that maximal therapeutic effect is achieved with low to medium doses of Revacept (40 mg and 120 mg).

Overall risk/benefit assessment

Revacept is a novel therapeutic agent that potently inhibits platelet aggregation at the site of atherosclerotic plaques without compromising systemic coagulation in animal models and healthy volunteers. No toxicities were observed during preclinical studies and no adverse reactions were observed when Revacept was administered to healthy human volunteers. Consequently, safety concerns are limited to adverse reactions specific to the target patient population and rare side effects.

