As for all antiplatelet drugs, it cannot be entirely excluded at this stage of development that Revacept could potentially increase bleeding propensity. Especially the likelihood of bleeding problems might occur in combination with multiple anti-thrombotic or antiplatelet drugs. In order to keep this risk low, concomitant oral anticoagulation and antiplatelet drugs other than anti-thrombotic monotherapy with Aspirin or Clopidogrel are prohibited in this study.

The immunogenicity of Revacept is judged to be considerably low, as its components are naturally occurring in the human body and should hence be recognised as 'self'. As for all therapeutic proteins, there is residual risk for Revacept triggering an aberrant immune reaction. Potential allergic responses may produce mild symptoms such as skin rashes and flue-like symptoms but also severe and potentially life-threatening reactions such as anaphylactic shocks. In order to minimise the risk of acute allergic reactions, patients with a history of allergic responses to intravenously administered drugs will be excluded from study participation. Furthermore, all patients will remain under medical supervision for 24 hours after receiving study medication.

Although the risk for production of anti-drug antibodies is low for single dose application, anti-Revacept autoantibodies could potentially cross-react with circulating platelets. For minimisation of this risk, patients with a known history of thrombocytopenia will not be

allowed to participate in this study. Furthermore, platelet counts and bleeding time will be closely monitored throughout the trial and blood samples for determination of anti-drug antibodies will be collected before and 3 months after exposure to study treatment.

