5. INVESTIGATIONAL PLAN

5.1. Study Design and Duration

This is a double-blind, placebo-controlled, randomised phase II study. Eligible subjects will be randomised to one of three treatment groups, receive study treatment and undergo endpoint evaluations. Follow ups are scheduled one and three days after treatment, 3 and 12 months.

The first 10 patients will be treated sequentially, e.g. only one patient is randomised at a time. The next patient will be randomised only once the first patient has completed visit 5 and no suspected unexpected serious adverse event has occurred. Prior to randomisation of a new subject, the Investigators must ensure that the patient randomised previously has completed visit 5 and not suffered a suspected unexpected serious adverse event. Once the first 10 patients have completed the sequential phase and the DSMB has recommended continuing the trial, parallel recruitment may start (see also section 1.3).

The study is conducted at a minimum of three study centres which will screen and recruit 150 eligible patients. During the recruitment period, each study centre is expected to provide the capacity and willingness to recruit at least 20 patients. There will be a competitive recruitment of patients, which means that some hospitals will enrol more than 20 patients and some less.

However, if a study centre randomises less than 3 patients in 9 months, further recruitment of patients may be stopped because the quality of a study is dependent on the number of patients per centre. Very few patients in a centre might be related to a higher rate of missing data or patient visits and a higher withdrawal rate.

The centres should have solid experience in clinical research and profound knowledge of GCP. Moreover, participating Investigators should have special interest in studying patients with carotid stenosis.

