5.2. Study Population

It is imperative that subjects fully meet all eligibility criteria.

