5.2.2. Exclusion Criteria

Subjects must not be included for any of the following reasons:

1) Sex and reproductive Status:

- WOCBP who are unwilling or unable to use an acceptable method to avoid pregnancy for up to 4 weeks after receiving investigational product.
- Women who are pregnant or breastfeeding
- Women with a positive pregnancy test on enrolment or prior to investigational product administration.

2) Target disease exceptions

- NIHSS score > 18
- Recent intracerebral haemorrhage by X-ray computed tomography (CT) or nuclear magnetic resonance (NMR)
- Cardiac cause of embolisation (atrial fibrillation or other cardiac source e.g. artificial

heart valves)

3) Medical history and concurrent disease

- History of hypersensitivity, contraindication or serious adverse reaction to inhibitors of platelet aggregation, hypersensitivity to related drugs (cross-allergy) or to any of the excipients in the study drug
- History or evidence of thrombocytopenia ($<30.000/\mu\text{l}$), bleeding diathesis or coagulopathy (pathological international normalised ratio (INR) or activated partial thromboplastin time (aPTT))
- Thrombolysis within the last 48 hours
- Relevant haemorrhagic transformation as determined by CT, NMR or anamnesis
- Oral anticoagulation or dual anti-platelet therapy with aspirin or clopidogrel and other P2Y inhibitors at screening (3 days for dipyridamole extended release; 8 hours for tirofiban/Aggrastat)
- Sustained hypertension (systolic BP >179 mmHg or diastolic BP >109 mmHg), hypertensive patients shall be treated in accordance with current guidelines for the management of arterial hypertension
- History of severe systemic disease such as terminal carcinoma, renal failure (or current creatinine >200 $\mu\text{mol/l}$), cirrhosis, severe dementia, or psychosis
- Current severe liver dysfunction (transaminase level greater than 5-fold over upper normal range limit)
- Active autoimmune disorder such as systemic lupus erythematosus, rheumatoid arthritis, vasculitis or glomerulonephritis
- Known atrial fibrillation or other clinically significant ECG abnormalities (at present)

4) Other Exclusion criteria

- Inability to provide informed consent (except for patient's legally responsible representative)
- Acoustic window that does not allow for TCD recording
- Participation in any other interventional study within less than 30 days prior to screening
- Suspected poor capability to follow instructions and cooperate

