6.1.7. Randomisation

Patients will be assigned to a treatment group by web-based online randomisation. Each patient will be allocated to one of the three treatment arms using a minimised randomisation method in order to balance potential prognostic factors between individual treatment arms. The following stratification factors will impact on treatment allocation:

- (1) Patient has received anti-platelet therapy with aspirin or clopidogrel prior to screening
 - No
 - Yes
- (2) Patient has received statin therapy prior to screening
 - No
 - Yes
- (3) Degree of carotid stenosis (ECST criteria)
 - 50-70%
 - > 70%

Once a patient is found to fulfil all eligibility criteria of the study the patient's identification number and details on concomitant medication are submitted to a web-based online randomisation program accessible at:

<https://www.randomizer.at/random/web/login.php>

All trial staff involved in patient randomisation will receive their log in data for the program after a short introduction to the system. In order to randomise a new patient, select "randomise" in the control panel on the left, enter the patient number (numeric format, including centre specific prefix, e.g. 01-005), select the applicable stratification

factors and click "randomise".

In case a reduced set of medication kit boxes is available at the study centre (e.g. due to damage or expiry of trial medication), you may tick option "reduced set of treatments", select "next", highlight all **unavailable** kit box numbers and then click on "randomise".

After successful randomisation of a patient, the web-based online system will send a confirmation email to the person who randomised the patient which contains the patient-specific random kit box number. This confirmation is to be printed, dated, signed and filed in the Investigator Site file.

Please check the number of remaining IMP kit boxes after each patient enrolment and make sure to request additional supplies as soon as less than 10 kit boxes remain, or earlier, in case of high recruitment rates.

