**Table 6-1: Definitions of protocol deviations**

No.	Criterion	Major deviation (violation)
1	Any of the inclusion criteria answered with 'No' Answers will be checked by other sources in the CRF - if possible	Yes or otherwise declared in the definitions in blind review report
2	Any of the exclusion criteria answered with 'Yes' Answers will be checked by other sources in the CRF - if possible	Yes or otherwise declared in the definitions in the blind review report
3	Patient did not receive the study medication as planned	Yes

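### Protocol Section 2 excludes patients with a history of allergy to intravenous drugs, but no eligibility list contains that criterion

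*Protocol*

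**What the plan says.** Section 2 (Overall risk/benefit assessment) accepts that a therapeutic protein can provoke allergic reactions, from rash to anaphylactic shock. It offers two measures against acute reactions. One is an exclusion: "patients with a history of allergic responses to intravenously administered drugs will be excluded from study participation". The other is observation: "all patients will remain under medical supervision for 24 hours after receiving study medication".

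Protocol 5.2.2 has one item on allergy. It covers a past hypersensitivity or serious reaction to platelet aggregation inhibitors, or a contraindication to them, and adds "hypersensitivity to related drugs (cross-allergy) or to any of the excipients in the study drug". The synopsis and SAP 6.3 carry the same item. The inclusion criteria in 5.2.1 say nothing about allergy.

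Three further places show how the lists are used. Protocol 5.2 opens with "It is imperative that subjects fully meet all eligibility criteria". Protocol 6.1.7 sets the condition for submitting a patient to the randomisation system: "Once a patient is found to fulfil all eligibility criteria of the study". In SAP Table 6-1, one of the deviations to be checked by program is "Any of the exclusion criteria answered with 'Yes", with answers verified against other CRF sources where possible.

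**The concern.** Section 2 presents the exclusion as settled and counts it among the reasons why the risk of an acute reaction is kept low. Those who approve the trial on that assessment would expect these patients to be kept out. Screening staff, however, work through a list of criteria, and the list does not ask the question.

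At stake is whether some patients receive an intravenous fusion protein although the protocol's own risk assessment says that they will not. A second consequence follows for the record. Because the deviation check is built on the same list, such an enrolment would leave no programmed trace, and the patient would stay in the per-protocol set by default.

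**Working it through.** No arithmetic applies, and the plan gives no figure to reproduce. The check compares the texts.

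**Step 1: the scope of each text.**

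| Allergy history | Section 2 | 5.2.2, synopsis, SAP 6.3 |
|---|---|---|
| Intravenous platelet inhibitor | Excluded | Excluded |
| Intravenous drug related to the study drug | Excluded | Excluded (cross-allergy) |
| Study drug excipient, given intravenously | Excluded | Excluded |
| Unrelated intravenous drug (for example an antibiotic or contrast agent) | Excluded | Not addressed |

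The listed item goes by type of agent and Section 2 goes by route. They overlap in the first three rows. The gap is the fourth row.

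**Step 2: whether the gap is an artefact.** The text of 5.2.1 and 5.2.2 is continuous and shows no redaction. The synopsis and SAP 6.3 independently carry the narrower item. The amendment history records a change of eligibility criteria in version 7.4 without details, so the documents do not show whether the criterion was once listed. Either way, the current texts disagree.

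**Step 3: whether Section 2 is only background.** The same assessment commits to keeping out patients with a known history of thrombocytopenia, and 5.2.2 has a matching criterion. Commitments of this kind were therefore meant to be carried into the list. The exclusion for intravenous-drug allergy was not carried over in its stated scope.

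**Step 4: follow one patient through the plan.** Take a patient with past anaphylaxis to an intravenous antibiotic.

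1. Section 2: excluded.
2. Screening against 5.2.1 and 5.2.2: no item is answered in a way that stops enrolment.
3. Randomisation under 6.1.7: goes ahead if the site takes the listed criteria as the full set.
4. SAP Table 6-1: no exclusion criterion is answered yes, so the program raises nothing.
5. Blinded data review (SAP 7.2): may classify the case, because its list of major deviations is expressly open-ended, but nothing points the review to it.

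**The case against.** **The list is silent, not permissive.** A reader might infer that 5.2.2 allows these patients in. It does not say so. It gives reasons for exclusion without stating that they are the only ones. Section 2 is itself protocol text, 4.1 and 10.7.1 require compliance with the protocol, and 6.1.7 does not cite 5.2.2. An investigator can satisfy both texts by applying the stricter one. This stands, and it limits the claim to what a site working from the list could do. It does not remove the problem, because a safety exclusion should not depend on sites recalling a sentence in the introduction.

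**Other safeguards exist.** There is partial cover in 5.2.2 (where related drugs are left undefined), 24-hour supervision, and a cautious start: "The first 10 patients will be treated sequentially, e.g. only one patient is randomised at a time". DSMB review comes before parallel recruitment, and randomisation stops at each SUSAR (protocol 1.3). General medical history is taken at screening and may bring an allergy to light. These limit the consequences. Apart from the partial cover and the chance that history-taking prompts an investigator to decline, they detect or manage a reaction and do not keep the patient from being dosed. The sequential phase covers 10 of the 150 planned patients. The 24-hour supervision appears in Section 2 but not in 6.1.6 or in the Visit 2 and 3 procedures, and Visit 3 may take place 2 hours after treatment.

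**The risk cannot be sized.** A reader might want to estimate how many such patients would be dosed, or infer that they react to Revacept more often. The documents give neither the frequency of these allergies nor any evidence of a higher reaction rate. Nor does phase I help: "30 male human volunteers received a single intravenous dose of Revacept ranging between 10-160 mg", without drug-related side effects, but the protocol does not say whether any volunteer had a drug allergy. This objection stands in full, and no number is offered here.

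**The analysis could still catch a case.** A reader might conclude from Table 6-1 that it could not. That is true of the programmed check only. SAP 7.2 leaves the blinded review free to act.

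**Conclusion.** The inconsistency is real. Section 2 promises an exclusion that 5.2.2, the synopsis and SAP 6.3 do not contain. The affected group is narrow: patients whose allergy is to an intravenous drug that is neither a platelet inhibitor, nor a related drug, nor an excipient. A site following the list could dose such a patient against the stated mitigation, and the programmed check would not show it.

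The conclusion rests on comparing the texts and on one assumption, that sites screen from the listed criteria. It does not show that any such patient was enrolled or harmed. How many could be affected is unknown. No endpoint, sample size or analysis method changes. The point should be fixed because it decides who is dosed and concerns a safeguard that the protocol itself invokes.

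**What to change.** Add *History of allergic response to any intravenously administered drug* to 5.2.2 under medical history and concurrent disease, to the synopsis, and to SAP 6.3. The criterion then becomes part of the check in SAP Table 6-1.

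Only if the sponsor did not intend this exclusion, correct the sentence in Section 2 and rest the mitigation on the narrower criterion and the 24-hour supervision. In that case the supervision should also be written into 6.1.6 or the Visit 2 procedures, since it would carry more weight.

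SAP 3.1 describes recruitment in the past tense. If enrolment has ended, the sponsor should state which text was intended. If it was Section 2, affected patients should be identified at the blinded data review (SAP 7.2) before unblinding and classified there. The documents show no dedicated allergy field, so this may need a query to the sites on top of the recorded medical history.

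The cost of either text change is a protocol amendment, which needs ethics committee approval before use (10.7.1). Adding the criterion also excludes some otherwise eligible patients. Their number is probably small, but the documents give no frequency from which to state it.

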3. STUDY ENDPOINTS

The **efficacy endpoints** are:

- to evaluate whether the incidence of preoperative microembolic signals (MES) is reduced in patients with symptomatic carotid artery stenosis who have been treated with Revacept plus antiplatelet monotherapy (aspirin or clopidogrel) versus antiplatelet monotherapy alone (placebo). MES will be assessed by transcranial Doppler (TCD) examination.(before and after treatment)
- Rate of MES per hour (before and after treatment)
- Assessment of neurological status (NIH Stroke Scale)
- Cerebral lesion analysis by DWI-NMR and correlation to neurological status (before and after treatment)
- Clinical endpoints will be summarised cumulatively i.e. before treatment, one and three days after treatment, at 3 months and at 12 months. The following endpoints will be recorded:
 - Rate of all cause death
 - Rate of stroke-related death
 - Any TIA, amaurosis fugax or stroke including haemorrhagic stroke
- Assessment of cardiovascular outcome including myocardial infarction and re-intervention up to 3 and 12 months

Safety objectives

To assess safety, adverse events will be continuously recorded and be overseen by an independent Data Safety Monitoring Board (see section 1.3).

Safety will be summarised by treatment group and include the following:

- Vital signs
- ECG parameters
- Anti-drug antibody titres
- Reporting AEs including wound healing complications, laboratory abnormalities and use of concomitant medication
- Haemostasis will be closely monitored by assessing:
 - laboratory parameters indicating thrombocytopenia and bleeding according to the RE-LY study group criteria
 - where feasible: in vitro platelet function with collagen, TRAP and ADP-mediated platelet aggregation and in vitro bleeding time by PFA-100 / PFA-200

4. ETHICAL CONSIDERATIONS

4.1. Good Clinical Practice

The investigation will be performed in accordance with the Declaration of Helsinki (1996), Good Clinical Practice (GCP), as defined by the International Conference on Harmonisation (ICH), in accordance with the ethical principles underlying European Directive 2001/20/EC and applicable local laws and regulations, in particular, the German GCP-Verordnung and Arzneimittelgesetz.

The study will be conducted in compliance with the protocol. The protocol and any

amendments and the subject informed consent will receive approval/favourable opinion of the German Bundesinstitut für Arzneimittel und Medizinprodukte (BfArM) (corresponding regulatory authority) and Independent Ethics Committee (IEC) prior to initiation of the study.

All potential serious breaches must be reported to advanceCOR GmbH immediately. A serious breach is a breach of the conditions and principles of GCP in connection with the study or the protocol, which is likely to affect, to a significant degree, the safety, physical or mental integrity of the subjects of the study or the scientific value of the study.

Study personnel involved in conducting this clinical trial will be qualified by education, training, and experience to perform their respective task(s). Systems with procedures that assure the quality of every aspect of the study will be implemented.

This study will not use services of study personnel where sanctions have been invoked or where there has been scientific misconduct or fraud (e.g. loss of medical licensure, debarment).

4.2. Independent Ethics Committee (IEC)

It is the responsibility of the Principal Investigator to obtain approval of the investigation plan/ amendments from the IEC and Regulatory Authorities according to local regulatory requirements. The Principal Investigator should file all correspondence with the IEC.

The Principal Investigator is responsible for keeping the IEC informed of the progress of the investigation and of any subsequent modifications to the protocol as deemed appropriate. This should be performed at least once annually. The Principal Investigator must also keep the IEC informed of any serious adverse reactions according to local regulatory requirements. In addition, the patient informed consent (or other appropriate document) should allow for release of the patient records for investigation documentation purposes.

4.3. Patient information and consent

It is the responsibility of the Investigator to give each patient (or the patient's legally responsible representative), prior to inclusion in the investigation, full and adequate verbal and written information regarding the objective and procedures of the study and the possible risks involved. Written informed consent must be obtained at screening in accordance with good clinical practice and local legislation prior to enrolment and randomisation.

After the written informed consent form and any other written information has been read and explained to the patient, the patient will sign and personally date the informed consent form. By signing the consent form, the patient attests that the information in the consent form and any other written information was accurately explained and apparently understood, and that the patient freely gave the informed consent. In addition, the Investigator who obtains the consent must sign and date the consent form.

The patients must be informed of their right to withdraw from the investigation at any time. Signed consent forms must remain in the Investigator Site File and must be available for verification by study monitors or local authorities at any time.

The informed consent and any other information provided to subjects, or, in those situations where consent cannot be given by subjects, the subject's legally acceptable representative, should be revised whenever important new information becomes available

[figure not shown]
that is relevant to the subject's consent, and should receive IEC approval/favourable opinion prior to use. The Investigator, or a person designated by the Investigator should fully inform the subject or the subject's legally acceptable representative of all pertinent aspects of the study and of any new information relevant to the subject's willingness to continue participation in the study. This communication should be documented. During a subject's participation in the study, any updates to the consent form and any updates to the written information will be provided to the subject.

